## **8.5. Tertiary Analyses**

After all primary, secondary, supporting and exploratory analyses are completed; the following tertiary analyses of the primary endpoint will be conducted. All analyses will be performed at a group level with respect to the following subsets of such analyses will be considered exploratory. Due to their exploratory nature these analyses will be viewed as descriptive, hypothesis generating, and will not involve formal hypothesis testing.

### **8.5.1. Irradiation of Platelets**

This exploratory analysis will summarize number and percent of irradiated PLTs transfused between arms. This may inform the effect of treatment with MIR PLTS versus Conventional PLTS that were irradiated between arms.

## 8.5.2. Washed Platelets

This exploratory analysis will summarize number and percent of washed PLTs transfused between arm. This may inform the effect of treatment with MIR PLTs versus Conventional PLTs that were washed between arms.

## 8.5.3. Age of Platelets

This exploratory analysis will summarize the age of PLTs transfused in days as a continuous variable between arms. This may inform the effect of treatment with MIR PLTs versus Conventional PLTs if there is a difference in the age of PLT units between arms. Platelet age is calculated as the date of the transfusion start recorded by the hospital site minus the Platelet Collection Date recorded by the blood center. For example, a platelet collected on the 10th of the month, and transfused on the 12th of the month would have an age of two (2) days.

## 8.6. Interim Analysis

An IA will be conducted at the 50% information fraction, i.e. when approximately 279 randomized mITT subjects have completed the post-transfusion period follow-up/early termination visit. The results of the IA will be presented to the study's Data Monitoring Committee (DMC). The DMC will assess efficacy, safety, and quality of trial conduct at the time of the IA.

Empirical conditional power [4] will be used in the IA to assess the futility in establishing NI. This will be carried out as follows.

A negative binomial model planned for the primary analysis will be fitted using unblinded data at the time of the IA following the convention for handling the off-protocol intervals prescribed in the primary analysis for each study arm. From these intercept only models, the estimates of  $\beta_0$  and the variance parameter  $\varphi$  will be obtained. For an individual to be recruited in the second half of the trial, this person's duration of time ( $t_i$ ) under observation will be drawn with replacement from each study arm's empirical distribution from the individuals who have completed their follow-up at the time of the IA regardless of on- or off-protocol intervals. The offset will be denoted as  $\ln(t_i)$ . Subjects whose time to transfusion independence is sampled and found to take place before Day 27 will be assumed to have zero bleeding days on the date of transfusion independence to Day 27 inclusive (which is assessed at the Post Transfusion follow-up visit). To simulate bleeding days over the period of transfusion dependence we first draw a random number  $V_i = \text{RAND}(\text{'GAMMA'}, 1/\varphi)$ , then compute  $U_i = V_i * \varphi$  such that  $U_i$  will be a gamma distributed with mean 1 and variance  $\varphi$ . The count response is then to be drawn from a Poisson distribution with mean  $U_i e^{\beta_0 + \ln(t_i)}$ . In order to simulate a count for the number of bleeding days which is guaranteed to be no greater than the number of bleeding assessment days for which bleeding data are required, a multinomial random variable will be generated with  $t_i + 1$  categories and probability vector  $P$  calculated based on the probability mass function of a right-truncated Poisson random variable. The resulting count will take on values 0, 1, 2, . . .,  $t_i$  while continuing to represent a realization of the bleeding data from the subject since it is using their estimated bleeding rate. When a cell probability for the multinomial is very small it will be set to  $1 \times 10^{-5}$  so that probabilities are  $> 0$  and to avoid computational errors caused by very small floating-point numbers. The count response drawn in this way will be a realization from the truncated negative binomial distribution.

A completed dataset will then be available with the first half of the sample representing individuals for whom data are recorded and the second half of the sample representing simulated data representing contributions from individuals yet to be recruited. A negative binomial model will be fitted to this complete dataset as described for the primary analysis. A Wald-based two-sided 95% confidence interval will then be constructed for the regression coefficient of the treatment indicator based on this completed dataset. It will then be recorded whether the upper limit of this confidence interval includes the value of  $\ln 1.6$  which defines the non-inferiority margin on the scale of the natural logarithm.

Ten thousand datasets will be computed in this way and the proportion of completed datasets for which the upper limit of a two-sided 95% confidence interval is below the value of  $\ln 1.6$  will be taken as the empirical conditional power. If this empirical conditional power is below 0.30 the guidance would suggest termination for futility, but this would not be a binding rule. Factors other than the empirical conditional power will be considered when weighing the futility of the study as a whole.

The DMC will be fully unblinded in its assessment of safety and efficacy data at the time of the formal IA. The IA tables will be prepared semi-blinded by treatment codes (e.g. Treatment A and Treatment B) and the actual treatment assignments will be provided to the DMC under separate cover.

Note that the power calculation does not consider the minor power loss due to the futility analysis. The study will not be stopped at the IA for a positive primary efficacy outcome (e.g. non-inferiority or superiority of MIRASOL).

The DMC will receive their routine unblinded DMC report at the IA. In addition, the following data will be included in the IA report:

A summary of the mean, SD, minimum and maximum days of grade 2 or higher bleeding and days of bleeding assessments will be included by treatment group alone and by treatment group and treatment type.

For the primary outcome of days of grade 2 or higher bleeding first a basic summary table will be presented of the average days of grade 2 or higher bleeding, and the average days of bleeding assessments per treatment group. Then a summary of estimates from the negative binomial model with the natural log of the estimate, standard error, and 95% CI will be presented. Last, a table testing the non-inferiority hypothesis will be included showing the estimate of MIRASOL versus CONTROL from the model, the natural log of the NI margin, standard error, and 95% CI.

The mean CCI at 1 hour (measured between  $\geq 10$  minutes and  $\leq 4$  hours) and the mean CCI at 24 hours (measured between  $\geq 18$  and  $< 30$  hours) after the end of every transfusion episode, when possible, will be calculated for each subject, and the mean of each treatment group will be presented along with differences in means for each pairwise comparison (treatment-control) at each time point (1 hour and  $> 18-30$  hours) as discussed in the analysis of Secondary Endpoint # 9. This will also be presented by age group (age  $< 18$ , 18-65 and  $> 65$  years) and treatment type (allogeneic transplant, autologous transplant, and chemotherapy).

Additionally, HLA antibody results are captured in a central laboratory database and will be maintained exclusively by BSRI. Blood System Research Institute will be responsible for reporting HLA results by treatment, age group, and treatment strata to the DMC.

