A negative binomial model planned for the primary analysis will be fitted using unblinded data at the time of the IA following the convention for handling the off-protocol intervals prescribed in the primary analysis for each study arm. From these intercept only models, the estimates of β_0 and the variance parameter φ will be obtained. For an individual to be recruited in the second half of the trial, this person's duration of time (t_i) under observation will be drawn with replacement from each study arm's empirical distribution from the individuals who have completed their follow-up at the time of the IA regardless of on- or off-protocol intervals. The offset will be denoted as $\ln(t_i)$. Subjects whose time to transfusion independence is sampled and found to take place before Day 27 will be assumed to have zero bleeding days on the date of transfusion independence to Day 27 inclusive (which is assessed at the Post Transfusion follow-up visit). To simulate bleeding days over the period of transfusion dependence we first draw a random number $V_i = \text{RAND}(\text{'GAMMA'}, 1/\varphi)$, then compute $U_i = V_i * \varphi$ such that U_i will be a gamma distributed with mean 1 and variance φ . The count response is then to be drawn from a Poisson distribution with mean $U_i e^{\beta_0 + \ln(t_i)}$. In order to simulate a count for the number of bleeding days which is guaranteed to be no greater than the number of bleeding assessment days for which bleeding data are required, a multinomial random variable will be generated with $t_i + 1$ categories and probability vector P calculated based on the probability mass function of a right-truncated Poisson random variable. The resulting count will take on values 0, 1, 2, . . ., t_i while continuing to represent a realization of the bleeding data from the subject since it is using their estimated bleeding rate. When a cell probability for the multinomial is very small it will be set to 1×10^{-5} so that probabilities are > 0 and to avoid computational errors caused by very small floating-point numbers. The count response drawn in this way will be a realization from the truncated negative binomial distribution.

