### 6.3.3. Sample Size

A total of approximately 558 mITT subjects will be randomized in a 1:1 fashion to MIRASOL:CONTROL. This sample size estimate accounts for 10% of subjects who are randomized but will never receive an on-study transfusion and thus, will not be included in the mITT analysis set and, therefore, the primary analysis. A total of 558 mITT subjects in MIRASOL versus CONTROL will provide approximately 85% power for establishing non-inferiority at the 1-tailed 0.025 level of significance (using a 2-sided 95% CI) accommodating a 10% relative increase in the mean rate of WHO grade 2 or higher bleeding (i.e.  $\mu_T / \mu_C = 1.1$ ).

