### 8.1.1. Primary Analysis

The MIRASOL vs CONTROL group will be compared with respect to the number of days of WHO grade 2 or higher bleeding. This will be carried out by fitting a negative binomial regression model with an offset defined as the natural logarithm ( $\ln$ ) of the number of days that bleeding was assessed in order to account for the fact that subjects may have different numbers of bleeding assessment days. As an example, if a subject had bleeding assessed on only 10 of 28 days, an “offset” of  $\ln(10)$  bleeding assessment days is incorporated into the linear predictor of the model. Similarly, if bleeding is assessed on each of the full 28 days of the planned treatment period, an offset of  $\ln(28)$  bleeding assessment days is incorporated. Adjustment using this offset will ensure that bleeding *rates* are calculated and compared between treatment groups and that the variable number of days with bleeding assessments across individuals is appropriately dealt with. Subjects who obtain transfusion independence prior to Day 28 will be assumed to have zero bleeding days between the date of transfusion independence and Day 27 and treated as if they had bleeding assessed on each of those days; these days will therefore contribute to the total number of bleeding assessment days used to calculate the offset. Subjects who drop-out of the study before Day 28 for reasons other than transfusion independence will contribute bleeding data for each of the days bleeding was assessed prior to the time of drop-out; bleeding status will not be simulated beyond the time of drop-out since the use of an appropriately computed offset deals with the variable duration of follow-up.

The handling of data following the administration of an off-protocol transfusion requires discussion. Here an off-protocol transfusion is defined as the transfusion of any kind of PLT product that differs from that to which the subject was randomized (i.e. MIRASOL or CONTROL).

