### 8.1.3. Assessment of Non-Inferiority and Superiority

An NI analysis will be carried out to assess the primary efficacy endpoint with the null hypothesis being the MIRASOL arm is inferior to the CONTROL arm and the alternative hypothesis being the MIRASOL arm is non-inferior to the CONTROL arm. The null ( $H_0$ ) and alternative ( $H_a$ ) hypotheses are defined as:

$$H_0: \frac{\lambda_T}{\lambda_C} \geq \delta \text{ and } H_a: \frac{\lambda_T}{\lambda_C} < \delta \text{ respectively}$$

where  $\lambda_T$  is the mean rate of the MIRASOL group,  $\lambda_C$  is the mean rate of the CONTROL group, and,  $\delta$  is the NI margin. To facilitate analysis, the null and alternative hypotheses are expressed on the natural logarithmic scale and take on the following forms.

$$H_0: \ln(\lambda_T) - \ln(\lambda_C) \geq \ln(\delta) \text{ and } H_a: \ln(\lambda_T) - \ln(\lambda_C) < \ln(\delta)$$

Specifically, a 95% confidence interval (CI) will be created about the point estimate (equivalent to a one-sided CI with an alpha level of 0.025) to test the null hypothesis, where the point estimate is defined as  $\ln(\lambda_T) - \ln(\lambda_C)$ . This parameter estimate will be obtained by fitting a negative binomial regression model with a natural log link, the response being the total number of WHO  $\geq 2$  grade bleeding days, a single treatment covariate which is 1 for individuals assigned to the MIRASOL product and 0 for those assigned the CONTROL, and with an offset of the  $\ln(\text{number the number of days bleeding was assessed})$ .

If the upper bound of the 95% CI is less than  $\ln(\delta)$ , then, NI of the MIRASOL arm relative to the CONTROL arm is inferred. Conversely, if the upper bound of the 95% CI is greater than or equal to  $\ln(\delta)$ , NI is not demonstrated. In this study, the NI margin is 1.6. Justification of the value of 1.6 for the NI margin is provided in the CIP.

If NI is demonstrated, superiority of the MIRASOL arm versus the CONTROL arm will be examined. Superiority of the MIRASOL arm compared to the CONTROL arm will be demonstrated if the upper bound of the 95% CI is less than zero ( $\ln(1)=0$ ).

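### The interim conditional-power simulation does not keep one time base: the bleeding rate comes from zero-filled days, but the counts are said to cover transfusion-dependent days only

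*SAP*

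**What the plan says.** SAP section 8.1.1 gives subjects who reach transfusion independence early zero bleeding days to Day 27 and treats those days as assessed: "these days will therefore contribute to the total number of bleeding assessment days used to calculate the offset". The fitted rate is therefore per zero-filled day.

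Section 8.6 fits that model at the interim, intercept only and by arm, to obtain β0 and φ. For each future subject it samples a time t_i from the arm's own distribution, sets the offset to ln(t_i), and draws a count with mean U_i·exp(β0 + ln t_i), capped at t_i. Three statements bear on what t_i covers:

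- The count is tied to dependence: "To simulate bleeding days over the period of transfusion dependence we first draw a random number".
- Subjects whose sampled time to independence falls before Day 27 are "assumed to have zero bleeding days on the date of transfusion independence to Day 27 inclusive".
- The real and simulated halves are then combined: "A negative binomial model will be fitted to this complete dataset as described for the primary analysis".

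Conditional power is the share of 10,000 completed datasets whose upper 95% limit lies below ln 1.6. A value below 0.30 suggests stopping for futility, without binding the committee. Section 8.6 of the Protocol document carries the same text ("To simulate bleeding days over the period of transfusion dependence"), so it is not separate support.

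**The concern.** A rate averaged over all assessed days, including the zeros after independence, belongs with all assessed days. If it is applied only to dependent days, and zero days are added afterwards, the same zeros dilute the simulated bleeding twice.

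Dependence time is also counted twice. Each arm's β0 already reflects how long that arm stayed dependent, so multiplying by arm-specific dependent days brings any arm difference in again. Days of platelet support is itself a secondary endpoint, so such a difference cannot be ruled out in advance. What is at stake is the one numerical futility guide the data monitoring committee receives.

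**Working it through.** **1. The plan's power figure.** Section 6.3.3 states that 558 mITT subjects "will provide approximately 85% power for establishing non-inferiority at the 1-tailed 0.025 level of significance", "accommodating a 10% relative increase in the mean rate of WHO grade 2 or higher bleeding" (ratio 1.1). Section 8.1.3 adds: "In this study, the NI margin is 1.6".

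- SE needed = ln(1.6/1.1)/(1.960 + 1.036) = 0.1250.
- With 279 per arm, SE² = [(1/μ_C)(1 + 1/1.1) + 2k]/279, where μ_C is the control mean and k the dispersion (φ in the SAP).

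The documents give neither μ_C nor k, so 85% can only be back-solved: k = 1.54, 1.80 and 1.94 for μ_C = 1.5, 2.5 and 4. For μ_C from 1.5 to 3.5 and k from 1 to 3, power runs from 0.64 to 0.975. I use μ_C = 2.5 and k = 1.8, which give SE = √(4.364/279) = 0.125.

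**2. Three readings of section 8.6.**

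- **A:** t_i includes the zero-filled days and the refit offset is the same. There is one time base.
- **B:** t_i is dependent days and the refit offset stays ln(t_i).
- **C:** t_i is dependent days, zero days are then added, and the refit uses the full assessed days (ln 28).

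**3. Arithmetic under C.** With 18 dependent days in control, a simulated control subject averages 2.5 × 18/28 = 1.61 bleeding days, or 64% of the intended 2.5. With a common offset of ln 28, the completed-data ratio is the ratio of arm means. Take an interim ratio of 1.25, so that the observed means are 2.5 and 3.125, and two equal halves:

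- **Both arms 18 days:** (3.125 + 2.009)/(2.5 + 1.607) = 1.25. The dilution cancels.
- **MIRASOL 20, CONTROL 18:** the simulated ratio is 1.25 × 20/18 = 1.39; completed, (3.125 + 2.232)/(2.5 + 1.607) = 1.30.
- **MIRASOL 18, CONTROL 20:** (3.125 + 2.009)/(2.5 + 1.786) = 1.20.

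The estimate must fall below ln 1.6 − 1.96·SE. Under A in the 20-versus-18 case, SE is 0.1245 and the limit is 0.2260. The centre, ln 1.25 = 0.2231, lies just below it, so conditional power is about one half. Under C, SE is 0.1294 and the limit is 0.2164. The centre, ln 1.304 = 0.266, lies 0.049 above it, so conditional power is well under one half.

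**4. Simulation.** 279 interim subjects, intercept-only fits by arm, gamma-Poisson counts truncated at t_i, refit, and Wald limit against ln 1.6. Each scenario used 60 interim datasets × 30 completions, with Monte Carlo error of about 1 to 2 points.

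| Interim ratio | Dependent days, MIRASOL / CONTROL | CP, A | CP, B | CP, C |
|---|---|---|---|---|
| 1.10 | 18 / 18 | 0.94 | 0.92 | 0.93 |
| 1.25 | 18 / 18 | 0.52 | 0.50 | 0.46 |
| 1.30 | 18 / 18 | 0.36 | 0.34 | 0.28 |
| 1.10 | 20 / 18 | 0.94 | 0.93 | 0.85 |
| 1.25 | 20 / 18 | 0.52 | 0.48 | 0.28 |
| 1.30 | 20 / 18 | 0.35 | 0.31 | 0.13 |
| 1.10 | 18 / 20 | 0.93 | 0.93 | 0.98 |
| 1.25 | 18 / 20 | 0.53 | 0.52 | 0.68 |

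With equal dependence, the loss under C comes with a larger SE (about 0.130 against 0.125), not a shifted ratio. At ratio 1.10 that loss is within Monte Carlo error. Off-protocol simulation, dropout and the 1×10⁻⁵ cell floor were not modelled.

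**The case against.** Section 8.6 introduces t_i as time under observation, writes the offset as ln(t_i), and caps the count at the assessment days for which bleeding data are needed. Section 8.1.1 treats post-independence days as assessed. If t_i is that same quantity, then β0, the simulated mean, the cap and the refit offset all agree and nothing is counted twice. Even if t_i is dependent days, keeping ln(t_i) as the refit offset preserves the rate ratio. Double counting needs dependent days, added zeros and a full-period refit offset together. The guide is also non-binding, other factors are weighed, and the committee sees the observed estimate with its confidence interval.

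Much of this stands. A reader might infer that conditional power is certainly computed wrongly, but the documents do not establish that, because t_i is never defined as dependent days. A reader might also infer that the procedure pushes the trial toward stopping. That holds only if MIRASOL dependence is longer or the arms are equal; with shorter MIRASOL dependence, conditional power rises. Nor does the shortfall in simulated bleeding days by itself shift the ratio, since it cancels when dependence is equal.

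The objection does not make the text consistent. If t_i already included the zero-filled days, the separate zero-fill step and the reference to the dependence period would do nothing. Section 8.6 itself speaks of sampling time to independence.

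**Conclusion.** The point holds as an inconsistent time base whose most natural reading counts post-independence zeros twice.

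- **Reading C:** conditional power is 1 to 8 points low with equal dependence, and moves by much more, in either direction, when dependence differs between arms. It can cross 0.30.
- **Reading B:** it is about 1 to 4 points low.
- **Reading A:** there is no numerical error, only wrong wording.

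These sizes rest on an assumed control mean, dispersion and dependence times, none of which the documents give. The crossings also need an unfavourable interim ratio, 1.25 or 1.30 in the cases run. There is no stop for efficacy, so the final non-inferiority test and type I error are untouched. It should be corrected, because following the written steps literally can mislead the futility assessment.

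**What to change.** Define t_i in section 8.6 as the same quantity used in the offset of the model that gave β0 and φ. Then choose one of two routes:

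- **(i)** Draw counts over total assessed days, including zero-filled days, and refit with that same offset. Delete the separate zero-fill step and the reference to the dependence period.
- **(ii)** Estimate β0 and φ with offset ln(dependent days), simulate over those days, then zero-fill and refit with the full assessed-day offset.

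If the interim analysis has already been run, record which reading was programmed. The cost is a few lines of SAP wording and a small edit to the interim program; no data collection or sample size changes.

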### 6.3.1. Primary Endpoint

The primary study objective will be assessed through examination of the Primary Efficacy Endpoint where clinical effectiveness will be measured by comparing the days of grade 2 or higher bleeding over the treatment period between the MIRASOL and CONTROL groups. Specifically, this study will investigate whether MIR-treated Aph PLTs (MIRASOL) are non-inferior to conventional PLTs (CONTROL) by testing the null hypothesis that the MIRASOL arm is inferior to the CONTROL arm. The null hypothesis will be tested using a one-sided alpha level of 0.025. If NI is established, superiority of MIR-treated Aph PLTs vs Conventional PLTs will be tested using a one-sided alpha level of 0.025 by employing a closed “gate keeper” multiple testing strategy. An in-depth discussion of the analysis of the primary efficacy endpoint is provided in Section 8.1 of this document.

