On occasions where a subject receives a mix of off-protocol and on-protocol units on the same day, they will be considered in an on-protocol period on that day. Transfusions can last more than one calendar day. The daily on- and off-protocol statuses will be assigned for the day the transfusion(s) starts. For subjects whose last transfusion is off-protocol, bleeding will be simulated until the subject completes the transfusion period or reaches transfusion independence. If the subject achieves transfusion independence prior to completing the transfusion period, the rules for transfusion independence will take over and subjects will be assumed to have zero bleeds and full follow-up from the day of transfusion independence until Day 27 inclusive (i.e. the remainder of the transfusion period).

Unless otherwise stated any subsequent analysis herein referring to the primary endpoint method will include the individualized simulated bleeding data for the off-protocol periods of time. This simulation will be done twice. Once at the IA and once at the final analysis. The set of simulations done for the primary efficacy analysis will be used for all subsequent analyses wherein off-protocol intervals are called to use simulated bleeding data.

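### The interim conditional power rests on one random draw of off-protocol bleeding counts that the final analysis will replace, so the futility figure can move with the seed alone

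*SAP*

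**What the plan says.** The file supplied as the protocol carries the same text as the SAP, so references are to the SAP.

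- **8.1.1, the draw.** For a subject with off-protocol intervals, observed bleeding on those days is replaced by a count from a right-truncated Poisson distribution. Its mean is the subject's own on-protocol bleeding rate times the number of off-protocol assessment days. A subject with an on-protocol rate of zero gets zero.
- **8.1.1, how often.** "This simulation will be done twice. Once at the IA and once at the final analysis". The set drawn for the primary efficacy analysis then serves every later analysis that calls for simulated off-protocol data.
- **8.6, interim models.** Intercept-only negative binomial models are fitted by arm, "following the convention for handling the off-protocol intervals prescribed in the primary analysis". They supply the intercept and dispersion from which future subjects are simulated.
- **8.6, completed datasets.** Each has "the first half of the sample representing individuals for whom data are recorded" and a simulated second half. The share of 10,000 such datasets whose upper 95% limit lies below ln 1.6 is the empirical conditional power. A value below 0.30 suggests termination for futility. The guide is non-binding and other factors are to be weighed.

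No step redraws the first-half off-protocol counts within the 10,000 datasets, and no seed is specified.

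**The concern.** The interim draw enters the calculation twice: as part of the fixed first half, and through the fitted intercept and dispersion that generate the second half. The final analysis will not contain that draw, because 8.1.1 has the simulation done again. The figure is therefore conditional on simulated noise as well as on patient data, and the same patients with another seed give another value. Running 10,000 datasets averages out the second-half noise but not this component.

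At stake is the stability of one number given to the DMC when it considers whether to end a 558-subject trial. Near 0.30, the guidance could change with the seed.

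**Working it through.** **Inputs from the SAP.** "The null hypothesis will be tested using a one-sided alpha level of 0.025" (6.3.1). The design "will provide approximately 85% power for establishing non-inferiority at the 1-tailed 0.025 level of significance", "accommodating a 10% relative increase in the mean rate of WHO grade 2 or higher bleeding", a ratio of 1.1 (6.3.3). "A total of approximately 558 mITT subjects will be randomized in a 1:1 fashion to MIRASOL:CONTROL", so 279 per arm (6.3.3). "In this study, the NI margin is 1.6" (8.1.3). The interim has about 279 subjects, or 139.5 per arm, with 10,000 datasets and the 0.30 guide (8.6).

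**Assumed, because the documents do not give them.** The share f of one arm's days that are off-protocol, the mean bleeding days m per 28, and the dispersion φ.

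**Step 1, the plan's own figure.** Without a rate or dispersion, the 85% power cannot be reproduced independently. It can be inverted:
- Final SE of the log rate ratio = (ln 1.6 − ln 1.1)/(1.960 + 1.036) = 0.3747/2.996 = 0.125.
- Interim SE = 0.125 × √2 = 0.177.
- With equal arms, φ = 279 × 0.125²/2 − 1/m, which is 1.68 at m = 2 and 1.93 at m = 4.

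**Step 2, conditional power in closed form.** For an interim log ratio d, under the current trend, CP = Φ((ln 1.6 − 1.96 × 0.125 − d)/(0.125/√2)) = Φ((0.225 − d)/0.0884).
- CP = 0.30 corresponds to d = 0.225 + 0.524 × 0.0884 = 0.271, a ratio of 1.31.
- At an interim ratio of 1.1, CP = Φ(0.1297/0.0884) = Φ(1.47) = 0.93.
- The slope at CP = 0.30 is 0.3477/0.0884 = 3.93 per log unit.

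**Step 3, seed noise, one arm affected.** The simulated days in the arm have mean and Poisson variance of about f·m·139.5, out of m·139.5 in total. The variance of d from the seed alone is then about f/(m × 139.5), ignoring truncation. For f = 5% and m = 2 this is 0.05/279 = 0.000179, SD 0.0134. Times 3.93, the SD of CP is 5.3 points.

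Seed SD of CP near 0.30, in percentage points:

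| f | m = 1 | m = 2 | m = 4 |
|---|---|---|---|
| 1% | 3.3 | 2.4 | 1.7 |
| 2% | 4.7 | 3.3 | 2.4 |
| 5% | 7.4 | 5.3 | 3.7 |
| 10% | 10.5 | 7.4 | 5.3 |

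Monte Carlo error at 0.30 is √(0.3 × 0.7/10,000) = 0.46 points.

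**Step 4, simulated draws.** Interim datasets of 279 subjects were generated at a true ratio of 1.3. Those with mean CP 0.15-0.50 were kept, and the off-protocol counts were redrawn by the truncated-Poisson rule with the closed-form CP of step 2.

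| MIRASOL subjects affected | Off-protocol days each | Share of arm-days | SD, m = 2 | SD, m = 4 |
|---|---|---|---|---|
| 15% | 5 | 0.15 × 5/28 = 2.7% | 3.3 | 2.2 |
| 30% | 7 | 0.30 × 7/28 = 7.5% | 5.4 | 3.8 |
| 50% | 10 | 0.50 × 10/28 = 17.9% | 8.2 | 5.2 |

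A reduced-scale run of the 8.6 algorithm itself gave 3.6, 5.0 and 7.8 points at m = 2, net of Monte Carlo error. It used 140 subjects per arm, all with 28 assessed days, 500 completed datasets per redraw, and 25 redraws in each of 5 interim datasets. The full 10,000-dataset procedure was not run.

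**Step 5, over all interims.** At a true ratio of 1.1, the CP z-score has mean 1.47 and SD 0.177/0.0884 = 2. The average slope is (1/√5) × φ_N(1.47/√5)/0.0884 = 0.447 × 0.322/0.0884 = 1.63, where φ_N is the standard normal density. At m = 2 the average seed SD is 1.4, 2.2 and 3.1 points for f = 2%, 5% and 10%. Across the step 4 scenarios it is about 1-4 points.

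**Step 6, disagreement about the guide.** Two seeds straddle 0.30 with probability of about (density of d at 0.271) × 1.128 × (seed SD of d). At a true ratio of 1.1 the density is 0.243/0.177 = 1.37. For m = 2 this gives 1.3%, 2.1% and 2.9% of trials at f = 2%, 5% and 10%. At a ratio of 1.3 it gives 2.2%, 3.4% and 4.8%. Over the wider set of scenarios the range is roughly 0.4-5.5%.

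**Step 7, effect of redrawing on the level.** Averaging over the draw turns Φ(z) into Φ(z/√(1 + s²/0.0884²)), with s the seed SD of d. From CP = 0.30 this gives 0.304 (f = 10%, m = 2, s = 0.0189) or 0.315 (f = 20%, m = 1, s = 0.0379).

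**The case against.** The strongest reply is that this is a small effect seen in its least favourable setting.

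- **The text does not say outright that the draw is frozen.** True. It is an inference from 8.1.1 and 8.6 together. But redrawing within the 10,000 datasets would conflict with the once-at-the-interim rule, so it is the natural reading.
- **The larger figures come from a selected band.** True. At a true ratio of 1.1 only about 13% of interims have CP between 0.15 and 0.50, and at 1.3 about 20%. An interim on its planning assumption has CP near 0.93, where the seed SD is about 1-3 points and the guide is not in play. No passage supports half of MIRASOL subjects spending 10 days off-protocol.
- **Monte Carlo error is a flattering comparator.** Partly true. At m = 2 and f = 2%, 5% and 10%, seed variance is only 0.2%, 0.6% and 1.1% of the interim estimate's sampling variance (for example 0.000179/0.177² = 0.6%). But sampling variation is what conditional power is meant to reflect. Seed noise carries no information and can be removed.
- **The guide is non-binding.** True, and this limits the harm to an unstable figure in front of the DMC.
- **The root is the single random imputation in the primary analysis.** Fair, but 8.6 can be repaired on its own.

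A reader might infer that the figure does move by several points in this trial. The documents do not support that, because they give no off-protocol share, bleeding rate or dispersion. A reader might also infer that the result is materially wrong as the chance of final success. Step 7 does not support that either: averaging over the draw hardly moves the level.

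**Conclusion.** The point holds as a conditional one. On the natural reading, the interim conditional power depends on one unrepeated random draw and an unspecified seed. With 15-50% of MIRASOL subjects having 5-10 off-protocol days and a mean of 2-4 bleeding days per 28, the seed SD is about 2-8 points when CP is 0.15-0.50. It averages about 1-4 points over all interims and is zero with no off-protocol days. These sizes also rest on the final SE of 0.125 back-solved from the stated 85% power.

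The defect is noise in a non-binding aid. It is not a material bias and not an automatic wrong stop. Type I error is not affected. It is a cheap improvement, worth making because the noise is greatest for figures near the guide.

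**What to change.** In 8.6, state that within each of the 10,000 completed datasets:
1. the off-protocol counts of first-half subjects are redrawn by the 8.1.1 rule;
2. the arm-specific intercept-only models are refitted;
3. the second half is simulated from those fits;
4. the primary model is fitted to the completed dataset.

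In 8.1.1, add a matching exception to the rule that the simulation is done twice and that one set serves later analyses. Pre-specify the seed. Seed variation in the conditional power then falls to Monte Carlo error, 0.46 points at 0.30.

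The cost is two SAP edits, programming and a longer run, because the two arm models are refitted for every dataset. No new data are needed. One drawback remains: the interim non-inferiority table in 8.6 would still rest on a single draw, so it would not correspond exactly to the averaged conditional power. The interim report should say so.
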